2.5.2 Statistical hypothesis, model, and method of analysis

The response rates for ORR at Cycle 7 Day 1, will be estimated on the Full Analysis Set (FAS) for all the patients, when all subjects have completed 1 year of treatment or discontinued earlier. Confidence intervals of 90% will be calculated based on the exact method ([Clopper and Pearson 1934](#)) for binomial distribution. Summary statistics (frequencies and percentages) will be provided. It is not planned to test any specific hypotheses related to the efficacy endpoint(s), but to provide estimates of efficacy endpoints in the pediatric population.

2.5.3 Handling of missing values/censoring/discontinuations

Patients with missing assessments that prevent the evaluation of the primary endpoint will be considered non-responders. This includes missing overall cGvHD response assessments at baseline and/or Cycle 7 Day 1. The time window for the Cycle 7 Day 1 visit is defined in [Table 2-1](#) above.

No data imputation will be applied. Patients who discontinue study treatment should return for the regular assessments indicated in Protocol Section 9.1. Addition or initiation of a new systemic therapy before Cycle 7 Day 1 will be considered a treatment failure, and patients will be counted as non-responder in the primary analysis.

2.5.4 Supportive analyses

Supportive analysis will include:

- A detailed description of response rates (CR, PR, Unchanged, mixed response and progression) at Cycle 7 Day 1
- A detailed description of the organ-specific response for all organs at Cycle 7 Day 1
- If at least 18 subjects are enrolled with either first line vs. SR-cGvHD respectively, the ORR will be explored for treatment naive and SR subgroup subjects.
This and further subgroups are described in [Section 2.2.1](#).

The supportive analyses will be performed on the FAS.

In addition, a sensitivity analysis will be done, where subjects with protocol deviations that may affect the primary endpoint are excluded from the analysis. These are following:

- Prohibited concomitant medication administered during treatment period (COMD01)
- Treatment naive or steroid refractory cGvHD corticosteroid treatment criteria not met (INCL04B)
- Missing individual organ assessment at C1D1 (unless not possible) (OTH02)
- Missing individual organ assessment at C4D1 or C7D1 (unless not possible) (OTH03)
- Starting dose of study drug (ruxolitinib) not per protocol-defined age-based schedule (Group 1 and 2) (TRT01)
- Starting dose of study drug (ruxolitinib) not per protocol-defined age-based schedule (Group 3 and 4) (TRT02)
- In treatment naive cGvHD subjects, in addition to ruxolitinib, methylprednisolone (or equivalent prednisone) treatment was initially not given as part of study treatment (TRT03)
- Patient did not take the ruxolitinib assigned dose (TRT08)
- The ruxolitinib dose assigned on C1D1 (based on age) was changed before the subject completed C7D1 assessments (excluding dose adjustments for safety) (TRT09)

- Corticosteroid taper was initiated earlier than allowed as per protocol (excluding dose adjustments for safety) (TRT13)
- Subject had a dose interruption of >21 days from ruxolitinib but was not permanently discontinued from ruxolitinib (WITH01)
- Individual organ response assessment / overall response assessment not as per protocol response criteria (OTH14)
- Patient was not compliant with study drug (Ruxolitinib); More than 7 days of consecutive insufficient treatment or overdosing or cumulated insufficient treatment over a period of 24 weeks is observed (TRT16)

Supportive analysis will be purely exploratory and are intended to explore the consistency of treatment effect. No inferential statistics (p-values) will be produced for the subgroups.

2.6 Analysis of the key secondary objective

No key secondary objective has been planned.

2.7 Analysis of secondary efficacy objective(s)

The secondary objectives in this study include the assessment of: failure free survival (FFS), ORR at Cycle 4 Day 1 (end of Cycle 3), duration of response (DOR), overall survival (OS), non-relapse mortality (NRM), best overall response (BOR), cumulative incidence of malignancy relapse/recurrence (MR), reduction and successful tapering of corticosteroid treatment (Cycle 7 Day 1) and graft failure.

2.7.1 Secondary endpoints

Failure Free Survival

FFS is a composite time to event endpoint incorporating the following FFS events: i) relapse or recurrence of underlying disease or death due of underlying disease, ii.) non-relapse mortality, or iii.) addition or initiation of another systemic therapy for cGvHD. If a patient did not experience any of these events, FFS will be censored at the latest contact data (on or before the cut-off date).

Best overall response (BOR)

Analyses of BOR at Cycle 7 Day 1 will not be repeated, whereas BOR up to end of study will be analyzed for the final CSR.

Best overall response (BOR) is defined as proportion of subjects who achieved overall response (CR or PR) at any time point up to and including Cycle 7 Day 1 and before the start of additional systemic therapy for cGvHD.

An additional analysis will include all response assessments up to End of Treatment of the subjects or data cut-off date and before the start of additional systemic therapy for cGvHD. Note,

for subjects who tapered off, all response assessments, including those collected after ruxolitinib discontinuation, will be considered for the analysis.

BOR will be calculated based on the FAS using local investigators' overall response assessments.

ORR at Cycle 4 Day 1 (end of Cycle 3)

Analysis of ORR at Cycle 4 Day 1 will not be repeated for the final CSR.

ORR at Cycle 4 Day 1, defined as the proportion of patients with complete response (CR) or partial response (PR), according to the NIH Consensus Criteria (Lee 2015). ORR will be calculated based on the FAS using local investigators' overall response assessed at the Cycle 4 Day 1 visit and taking into account initiation or addition of new systemic therapy before this time point.

Duration of Response

Duration of response (DOR) is assessed only for responders up to Cycle 7 Day 1 (i.e. all subjects with BOR = CR or PR considering response assessments up to Cycle 7 Day 1). DOR is defined as the time from first response until cGvHD progression, death, or the date of additional systemic therapies for cGvHD. Subjects without event will be censored at the date of their last response assessment prior to or at the analysis cut-off date if no events occurred on or before 12 weeks (84 days) after the last GvHD assessment.

An additional analysis of duration of response for responders up to data cut-off date will be done on all subjects with BOR considering all response assessments up to End of Treatment of the subjects or data cut-off date. Note, for subjects who tapered off, all response assessments up to End of Treatment even those collected after ruxolitinib discontinuation will be considered for the analysis.

Overall survival (OS)

Overall survival is defined as the time from date of treatment assignment to date of death due to any cause. If a patient is not known to have died, then OS will be censored at the latest date the patient was known to be alive (last contact date on or before the cut-off date).

Non-Relapse Mortality (NRM)

Non-relapse mortality (NRM), defined as the time from date of treatment assignment to date of death not preceded by underlying malignant or non-malignant disease relapse/recurrence. Underlying disease relapse/recurrence is considered as competing events. If a patient is not known to have died or experienced the competing event, then NRM will be censored at the latest date the patient was known to be event-free (last contact date on or before the cut-off date).

Incidence of Malignancy Relapse/Recurrence (MR)

Incidence of Malignancy Relapse/Recurrence (MR), defined as the time from date of treatment assignment to date of relapse/recurrence of the underlying hematologic malignancy disease. NRM is considered as competing event. If a patient is not known to have a hematologic malignancy relapse/recurrence or died without relapse/recurrence, then incidence of MR will

be censored at the latest date the patient was known to be event-free (last contact date on or before the cut-off date).

Reduction of daily corticosteroid dose

Reduction of daily corticosteroid dose, is defined as the proportion of patients with $\geq 50\%$ reduction from baseline in daily corticosteroid dose due to disease improvement at Cycle 7 Day 1.

For the final CSR the analyses will be done considering data up to end of study.

Reduction to low dose corticosteroids

Reduction to low dose corticosteroids, is defined as the proportion of subjects with reduction from baseline in daily corticosteroid dose to methylprednisolone-equivalent steroid dose of $\leq 0.2\text{mg/kg/day}$ (or equivalent dose of $\leq 0.25\text{mg/kg/day}$ prednisone or prednisolone) due to disease improvement at Cycle 7 Day 1.

For the final CSR the analyses will be done considering data up to end of study.

Graft Failure

This will be assessed by donor cell chimerism, defined as initial whole blood or marrow donor chimerism for those who had $\geq 5\%$ donor cell chimerism at baseline. If donor cell chimerism declines to $< 5\%$ on subsequent measurements, graft failure is declared.

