6.1.5 Treatment duration

The planned duration of study treatment is approximately 36 months (39 cycles).

The Treatment Period for each subject will begin on Cycle 1, Day 1 and continue until the end of Cycle 39 (Week 156), unless treatment change for any reason including treatment failure, e.g. cGvHD progression, mixed response or no response, or a GvHD flare as defined in [Section 6.1.5.2.1](#), intolerable toxicity, death, or withdrawal from the study for other reasons occurs.

During the Treatment period, the subjects' treatment will be managed according to their response as follows:

Subjects that achieve CR or PR: On Cycle 7 Day 1, subjects still receiving benefit from ruxolitinib may continue on ruxolitinib until the end of Cycle 39 (Week 156) and will follow the Visit Evaluation Schedule per [Table 8-1](#):

Subjects that achieve a CR or PR may taper corticosteroids at any time from two weeks of documented CR or PR. See [Section 6.1.5.2](#) for details

In subjects that achieve a CR or PR: A taper of ruxolitinib is allowed only on or after Cycle 7 Day 1.

- A taper of CNI is allowed after Cycle 7 Day 1.

Subjects who taper off ruxolitinib and all immunosuppressive therapy due to achieving a CR or PR will continue to follow the currently assigned Visit Evaluation Schedule ([Table 8-1](#)), including all safety and efficacy assessments, and will be monitored for cGvHD recurrence which must be reported in the database. Subjects experiencing cGvHD recurrence after tapering off ruxolitinib will be treated per Investigator discretion, which may include re-initiation of ruxolitinib and will follow the assigned Visit Evaluation Schedule ([Table 8-1](#)).

Subjects without CR or PR: If the subject is not receiving benefit from ruxolitinib therapy per investigator decision, the subject should discontinue ruxolitinib and be treated per institutional practice.

These subjects will enter the early discontinuation follow-up until completion of 39 cycles from their first dose of ruxolitinib.

Subjects who permanently discontinue ruxolitinib for reasons other than achieving a CR or PR prior to completion of 39 cycles on study will complete the safety follow-up visit and then follow the early discontinuation follow-up visit schedule (as described in [Table 8-1](#)). These subjects may be treated per Institutional practice.

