Functional status	SF36, FACT-BMT, and HAP are recommended Two-minute walk distance is recommended	SF36 or FACT-BMT plus HAP are strongly encouraged Two-minute walk distance provides prognostic information, consider assessing only at baseline
	Grip strength is recommended Karnofsky or Lansky performance status is recommended	No longer recommended Karnofsky or Lansky performance status is strongly encouraged only at baseline
Response Assignments		
Response category	Mixed response category is not recognized	Mixed response category is recognized and considered progression
Other	No comment on whether responses can be assessed in the setting of additional organ-directed treatments	If topical or organ-directed treatments are added, any CR or PR in those organs should be reported as occurring in the setting of additional local therapy.
	No comment on whether responses can be assessed in the setting of additional systemic immunosuppressive treatments	Addition of systemic immunosuppressive treatment is considered treatment failure, unless otherwise specified in the protocol

ALT indicates alanine transaminase; P-ROM, photographic range of motion; CHRI, Child Health Ratings Inventories; ASK, Activities Scale for Kids.

Table 2
2014 Recommended Chronic GVHD-Specific Core Measures for Assessing Responses in Chronic GVHD Trials

Measure	Clinician Assessed	Patient Reported
Assessments	NIH Skin Score (0-3) NIH Eye Score* (0-3) Modified OMRS (0-12) Total bilirubin (mg/dL), ALT (U/L) Alkaline phosphatase (U/L) FEV-1 (liters, % predicted) NIH Joint Score (0-3) P-ROM (4-25)	N/A
Symptoms	NIH Lung Symptom Score (0-3) Upper GI Response Score (0-3) Lower GI Response Score (0-3) Esophagus Response Score (0-3)	Lee Symptom Scale [7] (0-100) Skin itching (0-10) Mouth sensitivity (0-10) Chief eye complaint (0-10)
Global rating scales	None-mild-moderate-severe [7] (0-3) 0-10 severity scale [8] (0-10) 7 point change scale [9] (-3 to +3)	None-mild-moderate-severe [7] (0-3) 0-10 severity scale [8] (0-10) 7 point change scale [9] (-3 to +3)

OMRS indicates Oral Mucosa Rating Scale.

* Components include both signs and symptoms.

FORM A

Current Patient Weight: _____

Today's Date: _____

MR#/Name: _____

[figure not shown]
CHRONIC GVHD ACTIVITY ASSESSMENT- CLINICIAN

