16.4.2.1 Liver

Liver response assessment is based on the following chemistry lab parameters: Alanine aminotransferase (ALT), alkaline phosphatase (ALP) and total bilirubin (BILI). All three liver parameters must be obtained in order for the liver to be assessed.

Observed lab values and corresponding ULN at baseline should be documented. Observed post-baseline values will be compared to observed baseline values in order to determine the liver response for the post-baseline visit. The steps to apply the rules per NIH criteria and some examples are displayed in [Figure 16-1](#), [Figure 16-2](#) and [Figure 16-3](#).

Example 1 ([Figure 16-2](#)):

- At baseline ALT and AP are increased ($>$ ULN) and BILI is within the normal range.
- At the post-baseline visit ALT and BILI are within the normal ranges and the value of AP decreased from baseline by 56%: Therefore, the liver response for this visit is assessed as ‘partial response (PR)’.

Example 2 ([Figure 16-3](#)):

- At baseline Alkaline Phosphatase (AP) is increased ($>$ ULN), whereas ALT and BILI are within the normal range.
- At the post-baseline visit all 3 parameters are increased ($>$ ULN) but the absolute increase for each of the parameters is less than the corresponding value of $2 \times$ ULN. Therefore, the Week 4 liver response is considered as ‘unchanged’ from baseline.

Table 16-3 Response determination for chronic GvHD by organ at post-baseline assessment (comparison vs. baseline)

Organ	Complete response ¹	Partial response ¹	Progression ¹	No involvement/unchanged	
				Baseline	Post-baseline
Skin	NIH Skin Score 0 after previous involvement	Decrease in NIH Skin Score by 1 or more points	Increase in NIH Skin Score by 1 or more points, except 0 to 1	Score = 0	Score = 0 or 1
				Equal Scores at both time points	
Eyes	NIH Eye Score 0 after previous involvement	Decrease in NIH Eye Score by 1 or more points	Increase in NIH Eye Score by 1 or more points, except 0 to 1	Score = 0	Score = 0 or 1
				Equal Scores at both time points	
Mouth	NIH Modified OMRS 0 after previous involvement	Decrease in NIH Modified OMRS of 2 or more points	Increase in NIH Modified OMRS of 2 or more points	Equal OMRS at both time points (including Score=0) or change of OMRS from baseline less than 2 points	
Esophagus	NIH Esophagus Score 0 after previous involvement	Decrease in NIH Esophagus Score by 1 or more points	Increase in NIH Esophagus Score by 1 or more points, except 0 to 1	Score = 0	Score = 0 or 1

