16.4.3 Efficacy Assessments - Overall response assessment at one time point

Following the NIH working group recommendations the overall response evaluation (at each scheduled post-baseline time point/assessment) will be based on the evaluations for skin, eyes, mouth, esophagus, upper GI, lower GI, liver, lungs and joints/fascia. For each post-baseline assessment comparison will be made to baseline (C1D1).

- Complete response is defined as complete resolution of all signs and symptoms of cGvHD in all evaluable organs without addition of new systemic therapy, including CNIs.
- Partial response is defined as an improvement in at least one organ (e.g. improvement of 1 or more points on a 4 to 7 point scale, or an improvement of 2 or more points on a 10 to 12 point scale) without progression in other organs or sites, or initiation/addition of new systemic therapies.
- Lack of response is defined as unchanged, mixed response, or progression.
- Progression is defined as worsening of at least one organ and no improvement (CR or PR) in any other organ.
- Mixed response is a CR or PR in at least 1 organ accompanied by progression in another organ.
- Unchanged response is defined as stable disease or absence of improvement in any organ involved by cGvHD.

cGvHD Flare: is defined as any increase in symptoms or therapy for cGvHD after an initial response (CR or PR). A cGvHD flare is not considered a treatment failure unless a change of therapy or addition of another systemic treatment, including CNIs, occurs.

cGvHD Recurrence is defined as the return of cGvHD disease after tapering off study treatment due to response. Following completion of a taper of systemic therapy, if worsening of cGvHD symptoms occur, the patient is allowed to resume treatment for cGvHD as per local institutional practice. For the statistical analyses re-start of treatment for cGvHD is handled in the same way as addition or initiation of new systemic treatment.

Table 16-5 summarizes the rules for overall response assessment based on organ-specific evaluations at a scheduled post-baseline visit (e.g. the primary endpoint at Month 6 – Cycle 7 Day 1).

Table 16-5 Overall response evaluation

	Organ-specific response ¹				

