2.5.1 Primary endpoint

The primary efficacy variable of the study is **overall response rate (ORR)** at Cycle 7 Day 1, defined as the proportion of subjects demonstrating a complete response (CR) or partial response (PR), according to the NIH Consensus Criteria ([Lee et al 2015](#)) as reported in the CRF. Note that response is relative to the assessment of cGvHD at baseline.

- **Complete response** is defined as complete resolution of all signs and symptoms of cGvHD in all evaluable organs without initiation of any new systemic therapy.
- **Partial response** is defined as an improvement in at least one organ (e.g. improvement of 1 or more points on a 4 to 7 point scale, or an improvement of 2 or more points on a 10 to 12 point scale) without progression in other organs or sites, or initiation/ addition of new systemic therapies.
- **Lack of response** is defined as unchanged, mixed response, or progression. (Please refer to Table 8-3 and Table 16-3 in the protocol for the definitions of "unchanged", "mixed response" and "progression".)

cGvHD Flare and **cGvHD Recurrence** are not considered as a treatment failure, unless they require a change or addition of another systemic treatment defined as below.

- **cGvHD Flare** is defined as any increase in symptoms or therapy for cGvHD after an initial response (CR or PR). A cGvHD flare is not considered a treatment failure unless a change or addition of another systemic treatment, including CNIs, occurs.
- **cGvHD Recurrence** is defined as the return of cGvHD disease after tapering off study treatment due to response. Following completion of a taper of systemic therapy, if worsening of cGvHD symptoms occur, the patient is allowed to resume treatment for cGvHD as per local institutional practice. For the statistical analyses, re-start of treatment for cGvHD is handled in the same way as addition or initiation of new systemic treatment.

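### SAP 5.4.3 would miss treatment re-starts after taper-off that SAP 2.5.1 counts as new systemic therapy, which affects DOR, FFS and the BOR cut-off; a supplementary DOR ending at loss of response is a cheap addition

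*SAP*

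**What the plan says.** **Re-start.** SAP 2.5.1 defines recurrence as cGvHD coming back once study treatment has been tapered off for response. It directs that, for analysis, taking up cGvHD treatment again counts like starting a new systemic agent. Protocol 12.4.1 and 16.4.3 carry the same rule. SAP 5.4.3 is the operational definition of new or additional systemic therapy. It names two sources: the concomitant-medication page and the page for non-drug therapies and procedures.

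**DOR.** SAP 2.7.1: "DOR is defined as the time from first response until cGvHD progression, death, or the date of additional systemic therapies for cGvHD". Protocol Table 2-1 and 12.5.1 list the same events. New systemic therapy is also the third FFS component and the point after which responses stop counting for BOR.

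**Response categories.** Protocol 16.4.3 compares every visit with Cycle 1 Day 1 (C1D1). In protocol Table 16-3 the unchanged column for the 0-3 organ scores reads "Equal Scores at both time points", while skin progression is "Increase in NIH Skin Score by 1 or more points, except 0 to 1". For the overall category, protocol 16.4.3 says: "Progression is defined as worsening of at least one organ and no improvement (CR or PR) in any other organ". For ORR, SAP 2.5.1 says that lack of response "is defined as unchanged, mixed response, or progression".

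**The concern.** If the definition and the search rule disagree, two programmers can derive different event dates for the same subject and both follow the SAP. A subject who responded, tapered off, recurred and went back on ruxolitinib has an event under 2.5.1 and none under 5.4.3. DOR, FFS and BOR up to study end are all in the final report, so the disagreement reaches reported results.

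The second issue is interpretation. A reader may take DOR as time until response is lost. As listed, it is time until progression against C1D1, death or new therapy, and a responder can lose the whole improvement without meeting any of these.

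**Working it through.** The plan gives no figure for DOR to reproduce, so the check sets the rules side by side and traces example subjects.

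**Step 1: each re-start route after a completed taper-off.**

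| Route | SAP 2.5.1 | SAP 5.4.3 |
|---|---|---|
| Ruxolitinib | Event | Not found: protocol 6.2.1 keeps ruxolitinib off the concomitant-medication page |
| Systemic corticosteroid | Event | Not counted: interruptions and re-starts are expressly set aside |
| CNI given as treatment on C1D1, stopped, resumed | Event, if it is resumed cGvHD treatment | Not counted, expressly |
| Other agent, same pattern | Event, if it is resumed cGvHD treatment | Not counted: follows the CNI definitions |

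The last row should be nearly empty. Protocol 6.1 requires steroid-refractory subjects to stop other systemic cGvHD treatment before ruxolitinib, and treatment-naive subjects have had none beyond brief steroids.

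**Step 2: are re-starts foreseen, and are the data there?** Yes to both. Protocol 6.1.5 allows ruxolitinib to be resumed after recurrence. SAP 2.1.1 and 2.4.1 define on-treatment time and exposure for exactly these subjects and store the off-period as a dose interruption, with a reason that ties it to tapering after response. The re-start date is therefore in the exposure data.

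**Step 3: effect on one subject (illustration).** Visit days are from SAP Table 2-1: C4D1 = 85, C7D1 = 169, C9D1 = 225, C12D1 = 309, then every 84 days, so C18D1 = 309 + 2 × 84 = 477, and C39D1 = 1065. Days are counted inclusively, and C39D1 is taken as the last assessment. The subject first responds at day 85, tapers off, re-starts ruxolitinib at day 477 and never scores worse than C1D1.

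- Under 2.5.1: 477 − 85 + 1 = 393 days, event.
- Under 5.4.3: 1065 − 85 + 1 = 981 days, censored.

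**Step 4: which endpoints.**

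- DOR and FFS component iii change directly.
- The BOR cut-off moves, but a subject who tapered off for response has already responded. The CR-or-PR proportion should not change; the split between CR and PR could.
- The exploratory corticosteroid-free response rate (SAP 2.13) also depends on new therapy after recurrence, so the same clarification would settle it.
- ORR at C7D1 is hardly touched, because protocol 6.1.5 does not allow ruxolitinib or CNI taper before that visit.

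**Step 5: loss of response without a DOR event.** Take two organs with a 0-3 score, both 2 at baseline, PR at days 85 to 169, then a change at day 225 that persists, with no new therapy.

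| From day 225 | Overall category | Prespecified DOR | DOR ending at loss of CR/PR |
|---|---|---|---|
| Both organs back to 2 | Unchanged | 981 days, censored | 225 − 85 + 1 = 141 days, event |
| One organ at 1, the other at 3 | Mixed (protocol Table 8-3) | 981 days, censored | 141 days, event |

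**The case against.** **5.4.3 is later and more detailed, so it governs.** The SAP does not say so. It keeps both texts, and SAP section 4 lists only an added exploratory endpoint as a change from the protocol.

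**Recurrence is already analysed.** SAP 2.13 plans time to recurrence after ruxolitinib taper-off, or a listing if fewer than five subjects recur. This lowers the stakes, but it does not repair DOR or FFS.

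**The DOR event list is deliberate.** This stands. It is the same in protocol Table 2-1, protocol 12.5.1 and SAP 2.7.1, and comparison with C1D1 comes from the response criteria. Protocol 6.1.5.2.1 also makes it an explicit choice that steroid re-escalation for a flare is not treatment failure. Many real losses will still end DOR: protocol 6.1.5 has subjects leave treatment for "treatment failure, e.g. cGvHD progression, mixed response or no response", and a genuinely new agent is then an event. The gap concerns subjects kept on treatment or managed with existing agents.

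**Stronger readings that the documents do not support.**

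- That re-starts cannot be recovered. Only the 5.4.3 search misses them.
- That 5.4.3 ignores every CNI re-start. It counts a CNI taken up after C1D1 if the subject was not receiving it on C1D1, and prophylaxis that becomes treatment.
- That mixed response is progression for DOR, because the published table in protocol Appendix 3 says "Mixed response category is recognized and considered progression". Protocol 16.4.1 makes Appendix 4 the study's implementation, and SAP 2.5.1 refers to Table 8-3, where mixed is a separate category.
- That the primary result is at risk (Step 4).

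**Conclusion.** The mismatch between SAP 2.5.1 and 5.4.3 is a real error of specification: following 5.4.3 omits events that 2.5.1 declares. Ruxolitinib and corticosteroid re-starts are the main routes, with same-CNI re-start a narrower one. DOR and FFS are the endpoints to correct, and the BOR cut-off goes with them.

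The size cannot be computed. The documents give no number of subjects who tapered off, recurred and re-started. The 393 against 981 days above shows the direction for one constructed subject and is not an estimate. It assumes that no assessment before or after the re-start is progression against C1D1; if one were, DOR would end there under either rule.

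The loss-of-response point is a lesser one. The prespecified DOR is consistent across the documents and is not wrong; a supplementary analysis would make it easier to interpret. The 141 against 981 days is likewise an illustration only.

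**What to change.** **Needed.**

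1. Make SAP 5.4.3 agree with 2.5.1 on re-start after a completed taper-off, separately for ruxolitinib, corticosteroids, CNI and other agents. Distinguish this from steroid changes for a flare, which the plan already handles.
2. Where a re-start counts, add the study-treatment (exposure) pages to the 5.4.3 sources.
3. Apply one rule to DOR, FFS and BOR, and state any difference from the interim report.

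**Cheap improvement.**

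4. State in the SAP that mixed follows protocol Table 8-3 and is not progression in the prespecified DOR.
5. Keep that DOR and add a supplementary one ending at the first post-response assessment that is not CR or PR, at death, or at new systemic therapy. Show a second version in which the loss must still be present at the next assessment.

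**Cost.** Some re-programming on data already collected. The supplementary DOR will be shorter, and its unconfirmed version counts single-visit fluctuations as loss. If re-start is ruled an event, some subjects' DOR or FFS may differ from the interim report, and the change has to be explained.
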